## **11. LIST OF ABBREVIATIONS**

AE Adverse event

ALI Air-liquid-interface

---

AVI	Alanine-valine-isoleucine, non-functional TAAS2R38 allele
BUN	Blood urea nitrogen
CBC	Complete blood count
CBF	Ciliary beat frequency
CF	Cystic fibrosis
CI	Confidence interval
CRS	Chronic rhinosinusitis
DAF-FM	4-amino-5-methylamino-2',7'-difluorescein
eCRF	Electronic case report form
EDC	Electronic data capture
ERER	Event requiring expedited reporting
IB	Investigator's brochure
ICF	Informed consent form
IRB	Investigation review board
ITT	Intention-to-treat
L-NAME	L-N G -nitroarginine methyl ester
MOI	Multiplicity of infection
NO	Nitric oxide
NS	Not stated
PAV	Proline-alanine-valine, functional TAS2R38 allele
PHI	Personal health information
PID#	Participant identification designation number
PP	Per-protocol
PTC	Phenylthiocarbamide
QOL	Quality of Life
RUO	Research Use Only laboratory assay
SAE	Serious adverse event
SAP	Statistical analysis plan
SCC	Solitary chemosensory cells
SNP	Single nucleotide polymorphism
SUSAR	Suspected unexpected serious adverse reaction
TAS2R	Type 2 taste receptor, bitter taste receptor
TID	Thrice daily
USP	United States pharmacopeia

---

## LIST OF ABBREVIATIONS

AE	adverse event
ATC	Anatomical Therapeutic Chemical
BMI	body mass index
bpm	beats per minute
CRF	case report form
CSR	Clinical Study Report
DBP	diastolic blood pressure
ECG	electrocardiogram
ET	early termination
FDA	Food and Drug Administration
GI	gastrointestinal
HBsAg	hepatitis B surface antigen
HCV	hepatitis C virus
ICH	International Conference on Harmonisation
IP	Investigational Product
ITT	Intent-to-Treat
MedDRA	Medical Dictionary for Regulatory Activities
OTC	over-the-counter
PT	preferred term
SAE	serious adverse event
SBP	systolic blood pressure
SD	standard deviation
SOC	system organ class
TFLs	tables, figures, and listings
ULN	upper limit of normal
WHO	World Health Organization

## 1. INTRODUCTION

This document outlines the statistical methods to be implemented during the analyses of data collected within the scope of GeneOne Life Science Inc.'s Protocol T2R-002 [Efficacy, Safety, and Tolerability of GLS-1200 Topical Nasal Spray in the Prevention of Incident Confirmed SARS-CoV-2 Infection]. The purpose of this plan is to provide specific guidelines from which the statistical analyses will proceed. Any deviations from this plan will be documented in the clinical study report (CSR).

The reader is referred to the following complementary documents:

- Protocol T2R-002, version 7.0, dated 26Feb2021
- Case Report Form (CRF), version 1.017, dated 04Jun2020
- Symptom Diary, version 2, dated 16Apr2020
- Treatment Diary, version 1, dated 28 Mar2020
- DMP, version 1.0, dated 19Jun2020

## 2. STUDY OBJECTIVES

### 2.1. Primary Objectives

The primary objectives of the study are to evaluate the safety and tolerability of GLS-1200 topical nasal spray as well as the incidence in the diagnosis of PCR-confirmed SARS-CoV-2 infection by treatment group.

### 2.2. Secondary Objective

The secondary objective is to assess the documentation of symptoms consistent with SARS-CoV-2 infections relative to treatment group.

### 2.3. Exploratory Objective

The exploratory objective of the study is to assess the incidence of seroconversion in serum and the relationship of taste receptor genetics to incidence of SARS-CoV-2 infection relative to treatment group.

## 3. STUDY DESIGN AND PLAN

This is a Phase II, placebo-controlled, double-blind study of GLS-1200 topical nasal spray to assess the safety, tolerability, and ability to reduce the incidence of confirmed SARS-CoV-2 infection. Following recruitment and informed consent, those meeting enrollment criteria will be randomized 2:1 (GLS-1200:Placebo). Participants will initiate topical nasal spray applications immediately after randomization and will continue for 4 weeks. Participants will self-administer drug three times daily. Follow-up will continue through 6 weeks since some cases of SARS-CoV-2 infection may not be apparent until after the primary treatment period has concluded. The primary outcome measurements are safety, tolerability, and reduction in the diagnosis of PCR-confirmed SARS-CoV-2 infection. Secondary measures will assess the incidence of symptoms

between each visit, by treatment group. In addition the average number of days subjects experience each symptom will be summarized by treatment group. Exploratory measures will assess the incidence of seroconversion in serum and the relationship of taste receptor genetics to incidence of SARS-CoV-2 infection both relative to treatment group.

**Table 1: Schedule of Assessments**

Tests and Observations	Day 0	Week 2	Week 4	Week 6	Unscheduled
Permitted window (days)		±3d	±3d	±3d	N/A
Clinical Evaluations					
Obtain Written Informed Consent	X				
Confirm Eligibility Criteria	X				
Demographics	X				
Medical History and Concomitant Medications	X	X	X	X	
Physical Exam, height, weight, and Vital Signs 	X	X	X	X	X
Safety Evaluations					
Record Adverse Events		X	X	X	X
Provide participant diary	X				
Collect and review participant diary		X 	X	X	
Perform 12-lead ECG	X		X		
Pregnancy test 	X	X	X		
Blood for Hematology: CBC with differential	X		X		
Blood for Chemistry: Sodium, potassium, bicarbonate, glucose, BUN, Cr	X		X		
Study Related Procedures					
Dispense study drug & device, provide training	X				
Collect nasopharyngeal swabs for viral PCR	X	X	X	X	X
Collect serum for viral antibodies	X	X	X	X	
Collect plasma for measurement of quinine		X			
Collect saliva for TAS2R genotyping	X				
Estimated Blood Volume per Visit (mL)	40	25	40	20	

 A targeted physical exam will be performed at Weeks 2, 4 and 6 and at unscheduled visits.

 The participant diary will only be reviewed at Weeks 2 and 4; it will be reviewed and collected at Week 6.

 A urine pregnancy test will be administered.

#### **4. DETERMINATION OF SAMPLE SIZE**

The sample size for this study assumes an infection rate in the placebo group of 10%. A 2:1 randomization of 225 subjects would have a power of 80.8% to detect a difference of 9% between groups at alpha = 0.05 assuming 1% of individuals in the treatment group are confirmed to be infected with SARS-CoV-2.

#### **5. GENERAL ANALYSIS CONSIDERATIONS**

The statistical analysis results will be reported using tables, listings, and figures (TLFs). Summaries of continuous variables will display means, standard deviations (SDs), medians, minimums, maximums and the number of observations. Summaries of categorical variables will display frequency counts and percentages.

All analyses will be performed using SAS® Version 9.4 or higher.

#### **6. ANALYSIS POPULATIONS**

##### **6.1. Intent-to-treat (ITT) Population**

The ITT Population will include all randomized to treatment allocation.

##### **6.2. Safety Population**

The Safety Population will include all subjects who received at least one dose of study treatment.

##### **6.3. Per-protocol (PP) Population**

The PP Population will include all subjects who complete the trial and who receive  $\geq 90\%$  of the study treatments through to either diagnosis of SARS-CoV-2 infection (study end point) or to end of study (4 weeks), based on subject's completed doses on the treatment diary form, and who have no significant protocol deviations.

#### **7. STUDY POPULATION**

##### **7.1. Subject Disposition**

The number and percentage of subjects in each analysis population, who completed the study and who discontinued prior to study completion will be presented by treatment (GLS-1200 and placebo) and overall. Disposition will also be summarized by site. Subjects who discontinued prior to completing the study will also be summarized by reason for discontinuation.

Subject disposition will also be listed.

##### **7.2. Protocol Deviations**

Protocol deviations with significance will be listed.

### **7.3. Demographics and Baseline Characteristics**

Demographics, baseline data, vital signs, medical history, prior and concomitant medications and treatments will be summarized by means of descriptive statistics: continuous variables as mean, median, SD, minimum/maximum ranges and categorical variables as frequencies and percentages, stratified by treatment arms and overall, based on the ITT population. These summaries will also be provided by site. Demographic and baseline characteristics will be listed.

### **7.4. Medical History**

Medical history verbatim terms collected from the CRF will be mapped to system organ classes (SOCs) and preferred terms (PTs) using the Medical Dictionary for Regulatory Activities (MedDRA) (version 23.0).

Summaries (number and percentage of subjects) of medical history by SOC and PT will be provided by treatment and overall.

A listing of medical history will be provided.

### **7.5. Prior and Concomitant Medications**

Medication verbatim names collected from the CRF will be mapped to Anatomical Therapeutic Chemical (ATC) Classes and Preferred Names using the World Health Organization's WHO Drug Global March 2020 version. Preferred Names will consist of only the base compounds and not the salts (e.g., Naproxen Sodium will be listed only as Naproxen). Concomitant medications will be summarized for each treatment by ATC class and preferred name. Prior and concomitant medications will be listed.

A prior medication is defined as a medication that was administered up to 8 weeks prior to first dose of study treatment. All other medications will be considered concomitant.

### **7.6. Drug Exposure**

Exposure summaries of duration of exposure, total number of doses taken, and total number of doses missed, will be provided by treatment. Duration of exposure is defined as the date of last dose minus the date of first dose, regardless if any doses were missed in between.

Dosing data collected from treatment diaries will be listed along with any treatment side effects or device issues, and the number of known or suspected exposures to SARS-CoV-2.

### **7.7. Treatment Compliance**

Treatment compliance is defined as the total number of administered doses, as recorded in the treatment diary, divided by the total number of planned doses. Each recorded dose will be considered to be a complete dose of study drug. Descriptive statistics of treatment compliance as well as the proportion of subjects falling into different treatment compliance categories (<50%, 50%-80%, and >80%) will be summarized by treatment group.

Unless differences are observed between sites in the baseline characteristics and demographics that would confound interpretation of efficacy and safety results, all efficacy and safety will be summarized over both sites. If there are concerns for confounded results due to site differences in demographic or baseline characteristics, then all efficacy and safety results will be subset by sites as well as overall. However, no treatment comparisons within sites will be made since the study is not powered to assess treatment effect within sites.

## **8. EFFICACY ANALYSES**

### **8.1. Definition of the Primary Efficacy Endpoint**

The primary efficacy endpoint is the incidence of SARS-CoV-2 infection, confirmed by PCR at any time within four weeks of treatment initiation. Participants will be queried as to any new diagnosis of SARS-CoV-2 infection, defined as a positive PCR test for SARS-CoV-2. Subjects who test negative for SARS-CoV-2 infection at Weeks 2 and 4 will be considered treatment successes. Subjects who are lost to follow-up, require rescue therapy, discontinue the study prior to completion of Week 4, or test positive for SARS-CoV-2 infection at any point within four weeks of treatment initiation will be considered treatment failures. All deaths will be considered as treatment failures.

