### **8.1 Data Sets to be Analyzed**

Any participant who is randomized to a treatment allocation will be considered part of the intention-to-treat (ITT) population. The ITT population will be used for the summary of all demographic and baseline characteristics and for analysis of the primary outcome. Subjects lost to follow-up, requiring rescue therapy, those who discontinue study prior to completion of the primary treatment

end point (Week 4) and those who test positive for SARS-CoV-2 infection at Weeks 2 or 4 will be considered as treatment failures. Separate analysis will examine treatment failures in the period between the cessation of study treatment (Week 4) and the end of study (Week 6). All deaths will be considered as treatment failures. All subjects will be grouped in analyses and summaries based on their randomization allocation. The following analysis populations will be defined from the ITT population:

- The safety analysis set includes all randomized participants and is synonymous with the ITT set except that patients will be grouped based on treatment actually received.
- Per-protocol (PP) analysis set includes all participants who complete the trial and who receive ≥90% Study Treatments through to either diagnosis of SARS-CoV-2 infection (study end point) or to end of study for those without a SARS-CoV-2 diagnosis, based on subject completed accountability logs, and have no significant protocol violations. Participants in this sample will be grouped to treatment arms they actually received. This set will be used as a sensitivity analysis to summarize the primary and secondary efficacy outcomes.

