## **8.4 Efficacy Analysis**

The primary efficacy analysis is the difference between groups of confirmed SARS-CoV-2 infection as based on the ITT analysis population.

---

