## 8.7 Sample Size and Randomization

The sample size for this study is based on an infection rate in the placebo group of 10%. A 2:1 randomization of 225 subjects would have a power of 80.8% to detect a difference of 9% between groups at alpha = 0.05 assuming 1% of individuals in the treatment group was confirmed to be infected with SARS-CoV-2. [Table 8.7-1](#) below provides a range of treatment rates that could be detected with at least 80% power using this sample size.

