## 8.8 Missing Values

If a subject is lost to follow-up, or for some reason fails to provide an assessment of the primary endpoint, the subject will be considered a treatment failure per the ITT population.

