### **8.2. Analysis of the Primary Efficacy Endpoint**

The number and percentage of treatment failures as well as treatment successes will be presented by treatment and compared using Fisher's exact test. Additionally, the number and percentage of subjects who test positive as well as those who test negative for SARS-CoV-2 infection will be provided by treatment at each visit (Weeks 2, 4 and 6). This summary and analysis will be performed for both the ITT and PP populations.

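### The stated 80.8% power is for PCR-confirmed infection, but the primary ITT test compares treatment failure: at an assumed 5% non-infection failure per arm its power is about 45% to 54%, and no infection-only test or interval is prespecified in the ITT set

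*SAP*

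**What the plan says.** **Power.** Protocol 8.7 says that 225 participants randomised 2:1 "would have a power of 80.8% to detect a difference of 9% between groups at alpha = 0.05". SAP 4 repeats the calculation, "assuming 1% of individuals in the treatment group are confirmed to be infected with SARS-CoV-2". The columns of Protocol Table 8.7-1 are infection rates. Neither section mentions dropout or any other cause of failure.

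**Outcome as named.** Protocol 8.4 states: "The primary efficacy analysis is the difference between groups of confirmed SARS-CoV-2 infection as based on the ITT analysis population". It names no test and no interval. SAP 8.1 also opens by naming PCR-confirmed infection within four weeks as the endpoint.

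**Outcome as tested.** SAP 8.2 applies Fisher's exact test to treatment failures against successes. Under SAP 8.1 the failures include: "Subjects who are lost to follow-up, require rescue therapy, discontinue the study prior to completion of Week 4". Positive PCRs and all deaths are failures too. Protocol 8.1 has the same rule, in a list that begins "Subjects lost to follow-up, requiring rescue therapy, those who discontinue study prior to completion of the primary treatment". Under Protocol 8.8, when the primary endpoint is not assessed, "the subject will be considered a treatment failure per the ITT population". The shell of SAP Table 14.2.1.1 lists missing PCR results up to Week 4 as a further reason.

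**Infection on its own.** SAP 8.2 gives positives and negatives by visit as counts and percentages, and the table shell has a row for positives up to Week 4. Of the tests, SAP 8.2 says: "This summary and analysis will be performed for both the ITT and PP populations". Protocol 8.1 says of the per-protocol set: "This set will be used as a sensitivity analysis to summarize the primary and secondary efficacy outcomes".

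**The concern.** The power statement and the primary test concern different outcomes. Failures unrelated to infection add events to both arms, so the same 9-point difference in infection is harder to detect than the stated power suggests, and a null ITT result becomes more likely.

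If dropout differs by arm, the failure comparison can also move with no change in infection, in either direction. The table by reason would let a reader see this. But the plan holds no prespecified infection-only test, risk difference or interval in the ITT set with which to resolve it.

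**Working it through.** **Inputs.** From Protocol 8.7 and Table 8.7-1: 150 and 75 participants, infection 1% and 10%, alpha 0.05. From SAP 8.2: Fisher's exact test; sidedness and two-sided convention are not stated. The non-infection failure rate d is not in the documents, so every value below is an assumption.

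**1. Reproduce the stated power.** Sum Bin(x; 150, p1) × Bin(y; 75, p2) over all pairs (x, y) at which the test rejects.
- Method A rejects when the one-tail Fisher p-value is at most 0.025. For the six rows of Table 8.7-1 it gives 80.6, 80.9, 80.4, 80.4, 80.4 and 80.0%. The stated values are 80.3, 80.8, 80.3, 80.4, 80.3 and 80.0%.
- Method B uses the usual two-sided Fisher p-value, which adds up all tables no more probable than the observed one, at 0.05. It gives 87.6% for 1% against 10%, so it is not how 80.8% was obtained. It could still be the p-value reported.

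**2. Power of the failure test, equal d in both arms.** If other failures are independent of infection, the failure rate is 1 − (1 − p)(1 − d). At d = 5% this is 1 − 0.99 × 0.95 = 5.95% against 1 − 0.90 × 0.95 = 14.5%. If the two simply add, it is p + d, or 6% against 15%.

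| Assumed d | A, independent | A, additive | B, independent | B, additive |
|---|---|---|---|---|
| 0% | 80.9% | 80.9% | 87.6% | 87.6% |
| 1% | 70.2% | 70.8% | 77.5% | 78.0% |
| 2% | 61.4% | 62.8% | 69.2% | 70.4% |
| 5% | 45.0% | 48.4% | 51.1% | 54.5% |
| 10% | 30.5% | 36.3% | 34.2% | 40.1% |
| 20% | 18.4% | 26.6% | 20.1% | 28.9% |

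**3. A fixed small number of failures.** Place k non-infection failures at random among the 225 and let the rest be infected at 1% or 10%. One failure gives 76.0% by A (82.7% by B); two give 71.1% (77.8%).

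**4. Unequal dropout, independent of infection.**
- No drug effect, 5% infected per arm, dropout 5% active and 10% placebo: failure is 1 − 0.95 × 0.95 = 9.75% against 1 − 0.95 × 0.90 = 14.5%. The test favours GLS-1200 in 13.2% of trials by A (16.4% by B). With equal 5% dropout it does so in 1.4% (2.1%).
- True infection 1% against 10%, dropout 10% active and 5% placebo: failure is 1 − 0.99 × 0.90 = 10.9% against 1 − 0.90 × 0.95 = 14.5%. Power is 8.4% (10.7%).

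**5. What the per-protocol repeat supplies.** Table 14.1.1.1, footnote 3, defines trial completion as reaching Week 4 or having a PCR-confirmed infection. Uninfected people who leave early are therefore excluded, and only rescue therapy or a missing PCR could remain as a non-infection failure. The set also requires at least 90% of doses and no significant deviation, and no interval is planned.

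**6. Observed infection over all randomised participants.** Suppose nobody is positive at baseline and every lost participant's infection goes unseen. The rates are then p × (1 − d): 0.95% against 9.5% at 5% loss, 0.9% against 9.0% at 10%, and 0.8% against 8.0% at 20%. Power is 78.3, 75.3 and 68.5% by A (86.0, 84.2 and 79.9% by B). In the two cases of step 4, this comparison favours GLS-1200 in 0.9% (1.8%) of trials with no effect, and has 79.2% (86.9%) power with the true effect.

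**The case against.** The strongest defence is that counting missing outcomes as failures is a recognised rule, that both documents state it openly, and that Table 14.2.1.1 breaks the failures down by reason and arm. All of that stands. A reader might infer that the rule is itself an error or is hidden, and the documents do not support that. The gap lies in the power statement and in the missing infection-only ITT comparison.

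Three further inferences would go too far.
- **That the trial has 45% power.** The 5% is assumed, and 45% is the lowest of four defensible figures at that rate. Matching Table 8.7-1 shows how the power was computed, not which Fisher p-value will be reported.
- **That any infection-only p-value would be post hoc.** The per-protocol repeat prespecifies one that is nearly infection-only. It does so in a set selected after randomisation, which Protocol 8.1 calls a sensitivity analysis, and without an interval.
- **That one or two stray failures are harmless.** Power stays above 80% with one failure only under method B, which starts at 87.6% and is not the basis of the stated figure.

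Nor is there a contradiction over a missed Week 2 swab: SAP 8.1, footnote 2 and the table row all make it a non-success. Only Day 0 is ambiguous. Someone who missed just that swab meets footnote 2 as a success, but also meets the row on missing PCR at any visit up to Week 4, which footnote 3 makes a failure.

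**Conclusion.** The mismatch is real and should be fixed. The 80.8% describes infection with essentially no other failures. It does not describe the primary test once such failures occur.

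With an equal assumed rate in both arms, the power to detect 1% against 10% infection is about 70% to 78% at 1%, 45% to 54% at 5%, 30% to 40% at 10% and 18% to 29% at 20%. The spread reflects the unstated Fisher convention and whether other failures are independent of infection or additive. The direction does not depend on these choices: every variant is below 80% at 1%.

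In the two unequal-dropout examples, the test favours an ineffective drug in 13% to 16% of trials, and has only 8% to 11% power for the planned effect. These examples rest on assumed dropout and do not predict what this trial will see.

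**What to change.** 1. **Protocol 8.7 and SAP 4.** State that 80.8% is the power for infection with no non-infection failures. Tabulate the power of the failure test over an assumed range, for example 1% to 20%, and name the Fisher convention.
2. **SAP 8.2 and Table 14.2.1.1.** Keep the ITT failure test unchanged. Add a prespecified supportive Fisher test of observed PCR-confirmed infection through Week 4 among all randomised participants who were not PCR-positive at baseline, with the risk difference and exact 95% confidence interval. The baseline condition is needed because Protocol 6.5 asks people who are positive at enrolment to remain in the study. A missing Day 0 swab does not exclude anyone, and every confirmed positive counts whether or not the participant returns at Week 4.
3. **Sensitivity analysis.** Repeat the supportive test in those with a Week 4 PCR result or an earlier positive, or in those with a Week 4 result only, and state the missingness assumption. The former slightly inflates the rate. If half of infections are seen by Week 2 and 5% leave later, a true 10% becomes (0.05 + 0.05 × 0.95) / (0.05 + 0.95 × 0.95) = 10.2%. The latter drops early positives who do not return.
4. **Minor.** Make the missing-PCR row of Table 14.2.1.1 refer to Weeks 2 and 4, so that it agrees with SAP 8.1 and footnote 2.

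The cost is some wording and one block of table rows. There are two downsides. The power statement becomes less favourable. And the supportive test treats unseen infections in dropouts as non-events, so it understates incidence where dropout is higher.

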>80%	x (xx.x%)	x (xx.x%)

Site 101

.

Site 108

.

[1] Duration of exposure is defined as the date of last dose minus the date of first dose + 1.

[2] Treatment compliance is defined as the total number of doses taken divided by the total number of planned doses times 100.

Reference: Listing 16.2.5.1 and Listing 16.2.1

Table 14.2.1.1  
Incidence of SARS-CoV-2 Infection by Visit  
(ITT Population)

	GLS-1200 (N=XX)	Placebo (N=XX)	p-value [1]
Treatment Success [2]	x (xx.x%)	x (xx.x%)	
Treatment Failure [3]	x (xx.x%)	x (xx.x%)	
Lost to follow-up	x (xx.x%)	x (xx.x%)	
Required rescue therapy	x (xx.x%)	x (xx.x%)	
Discontinued study prior to completion of Week 4	x (xx.x%)	x (xx.x%)	
Tested positive for SARS-CoV-2 infection at any time up to Week 4	x (xx.x%)	x (xx.x%)	
Had missing PCR result at any visit up to Week 4	x (xx.x%)	x (xx.x%)	
Died	x (xx.x%)	x (xx.x%)	
Week 0 PCR Result			
n	x	x	
Negative	x (xx.x%)	x (xx.x%)	
Positive	x (xx.x%)	x (xx.x%)	
Missing	x (xx.x%)	x (xx.x%)	
Week 2 PCR Result			
n	x	x	
Negative	x (xx.x%)	x (xx.x%)	
Positive	x (xx.x%)	x (xx.x%)	
Missing	x (xx.x%)	x (xx.x%)	
...			

[1] The p-value is calculated using a Fisher's exact test.

[2] Subjects who test negative for SARS-CoV-2 infection at Weeks 2 and 4 are considered treatment successes.

[3] Subjects who met any of the reasons listed are considered treatment failures. Subjects who fail treatment for multiple reasons are counted once for each reason.

Reference: Listing 16.2.6.1

Source: \\xx\\xxx\\xxx\\xxx\\xxxxxx\\xxxxxxxxxxxx\\xxxx\\xxxxx.sas      date      time

**Programming note: Continue for remaining visits. Repeat for Table 14.2.1.2 Incidence of SARS-CoV-2 Infection (PP Population).**

Table 14.2.2  
Incidence of Individual Symptoms and Average Number of Days with Symptoms by Visit Interval  
(ITT Population)

Symptom	GLS-1200 (N=XX)	Placebo (N=XX)
Subjects who reported Body Aches at least once from Day 1 to Week 2	x (xx.x%)	x (xx.x%)
Subjects who reported Body Aches at least once from Week 2 to Week 4	x (xx.x%)	x (xx.x%)
Subjects who reported Body Aches at least once from Week 4 to Week 6	x (xx.x%)	x (xx.x%)
Subjects who reported Body Aches at least once during the overall treatment phase [1]	x (xx.x%)	x (xx.x%)
Number of days subjects reported Body Aches from Day 1 to Week 2		
n	x	x
Mean (SD)	xx.x (xx.xx)	xx.x (xx.xx)
Median	xx.x	xx.x
Min, Max	xx, xx	xx, xx
Number of days subjects reported Body Aches from Week 2 to Week 4		
n	x	x
Mean (SD)	xx.x (xx.xx)	xx.x (xx.xx)

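### Loss to follow-up, rescue therapy and death have no clear Week 4 limit in the primary endpoint, so some participants meet both the success rule and the failure rule

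*SAP*

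**What the plan says.** SAP 8.1 defines the primary endpoint as infection "confirmed by PCR at any time within four weeks of treatment initiation". It then gives three rules.

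- Success: "Subjects who test negative for SARS-CoV-2 infection at Weeks 2 and 4 will be considered treatment successes". No later event is excepted.
- Failure: "Subjects who are lost to follow-up, require rescue therapy, discontinue the study prior to completion of Week 4, or test positive for SARS-CoV-2 infection", and the sentence ends "at any point within four weeks of treatment initiation will be considered treatment failures".
- Death, in a sentence of its own: "All deaths will be considered as treatment failures".

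The shell for Table 14.2.1.1 (SAP Appendix C) lists six failure reasons. Three carry a Week 4 limit: discontinuation, missing PCR, and "Tested positive for SARS-CoV-2 infection at any time up to Week 4". Three carry none: lost to follow-up, required rescue therapy, and died. Footnote [2] repeats the success rule. Footnote [3] makes anyone who meets any listed reason a failure. Table 14.2.1.2 repeats the layout for the per-protocol population.

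Protocol 8.1 leaves the same items undated but adds: "Separate analysis will examine treatment failures in the period between the cessation of study treatment (Week 4) and the end of study (Week 6"). Protocol 8.8 assigns failure as follows: "If a subject is lost to follow-up, or for some reason fails to provide an assessment of the primary endpoint", again without a date. The only Week 4 to 6 efficacy output on infection status that SAP 8.2 plans is the count of PCR results at Week 6.

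**The concern.** The endpoint is fully observed once the Week 4 swab is in. An event after that should not change a participant's primary classification, and for PCR-confirmed infection it does not: a first positive at Week 6 is outside the window. For loss to follow-up, rescue therapy and death the text leaves this open. If they count, a Week 5 loss is a primary failure and a Week 5 infection is not, which makes little sense for an infection endpoint.

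Two programmers could code the same participant differently from this SAP, and the choice might be made after the results are known. Few infections are expected (about 9 in 225), so a handful of recoded participants matters. If late events differ by arm, the comparison is biased as well as diluted.

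**Working it through.** **1. Who is affected.** Take a participant with negative PCR at Weeks 2 and 4, then an event between Week 4 and Week 6.

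| Late event | Success rule (SAP 8.1, footnote [2]) | Failure rule (SAP 8.1, footnote [3]) |
|---|---|---|
| PCR positive at Week 6 | Met | Not met: limited to Week 4 |
| Discontinues | Met | Not met: limited to before Week 4 |
| Week 6 swab missing only | Met | Not met: limited to Week 4 |
| Lost to follow-up | Met | Met in the table; unclear in the text |
| Rescue therapy | Met | Met in the table; unclear in the text |
| Dies | Met | Met in both |

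The last three rows satisfy both rules. Neither SAP 8.1 nor the table says which prevails.

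**2. The plan's own power figure.** Inputs from SAP 4 and SAP 8.2: 150 v 75, infection 1% v 10%, alpha 0.05, Fisher's exact test. Enumerating every pair of counts and rejecting when the one-tail Fisher probability is at most 0.025 gives 80.9%, against 80.8% stated. The same rule reproduces all six rows of Protocol Table 8.7-1 within 0.4 points. (The usual two-sided Fisher p, summing probabilities, gives 87.6%.) Expected infections: 150 × 0.01 + 75 × 0.10 = 1.5 + 7.5 = 9.

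**3. Equal late events coded as failures.** The documents give no late-event rate, so L below is assumed. Failure rate = 1 − (1 − infection rate)(1 − L), with no other non-infection failures.

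| L in both arms | Active | Placebo | Power |
|---|---|---|---|
| 0 | 1.00% | 10.0% | 80.9% |
| 1% | 1.99% | 10.9% | 70.2% |
| 2% | 2.98% | 11.8% | 61.4% |
| 3% | 3.97% | 12.7% | 54.8% |
| 5% | 5.95% | 14.5% | 45.0% |

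At L = 5%, late recodes number 150 × 0.99 × 0.05 + 75 × 0.90 × 0.05 = 7.4 + 3.4 = 10.8. Expected failures total 19.8, so they are about 55% of the total.

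**4. With early non-infection failures already present.** The endpoint also fails participants lost, discontinued or missing a swab before Week 4. Let E be that rate (assumed), so failure rate = 1 − (1 − infection rate)(1 − E)(1 − L).

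- E = 5%: 5.95% v 14.5%, power 45.0%. Adding L = 2%: 7.83% v 16.21%, power 38.2%.
- E = 10%: power 30.5%. Adding L = 2%: 27.3%.

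**5. Unequal late events (assumed).**

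- No true effect, 10% infection in both arms, late loss 5% active v 10% placebo: failure rates 0.10 + 0.90 × 0.05 = 14.5% and 0.10 + 0.90 × 0.10 = 19.0%. The test falsely favours active 10.2% of the time, against at most 2.5% nominal.
- True 1% v 10%, late loss 5% active v 2% placebo: failure rates 5.95% v 11.8%, power 24.1%.

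**The case against.** The strongest reply is that the plan already implies a Week 4 limit. SAP 8.1 opens with a four-week window and calls anyone negative at Weeks 2 and 4 a success without exception. The closing four-week phrase in the failure sentence can be read as governing the whole list. Protocol 8.1 sends later failures to a separate analysis. Protocol 8.8 sits under missing values, where loss reads naturally as one way of lacking the primary assessment.

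Much of this stands. A reader might infer from footnote [3] that participants observed negative definitely become failures. The documents do not support that: they give two conflicting rules and no precedence. A reader might also infer that anyone who simply misses Week 6 fails. Protocol 4.4 ties loss to follow-up to not returning and not being located, or not responding to contact, so a missed visit alone is not enough. Nor can late events be called unrelated to infection: a death may follow from it, and rescue therapy is undefined in both documents.

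On size, the 20-point loss at a 2% late-event rate holds only if nothing else before Week 4 produces non-infection failures; with 5% early failures it is about 7 points. Individual examples can also mislead. With the usual two-sided Fisher p, adding 4 active and 2 placebo late losses moves 2 v 6 infections from 0.018 to 0.076, but moves 2 v 8 only from 0.003 to 0.014.

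The reply does not remove the overlap. If the closing phrase covered the whole list, the separate Week 4 limit on discontinuation would be largely redundant. It cannot reach the death sentence. And the table shell, which programmers will follow, dates three rows and leaves three undated.

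**Conclusion.** The point holds as an unresolved overlap in the primary endpoint definition. Death has no Week 4 limit on any reading; loss to follow-up and rescue therapy have none that is clear. Participants with such an event between Weeks 4 and 6 after negative swabs are both successes and failures as written.

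The size depends on an unknown late-event rate and on the failure coding being chosen. With 2% late events in both arms, the cost is about 20 points of power with no other non-infection failures and about 7 points with 5% of them before Week 4. The more serious risk is bias when late events differ by arm. The stated 80.8% is not wrong; it simply allows for no failures other than infection. The correction is still worth making before analysis, because it decides who counts as a primary event and costs almost nothing.

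**What to change.** - In SAP 8.1, Tables 14.2.1.1 and 14.2.1.2, and Protocol 8.1 and 8.8, limit loss to follow-up, rescue therapy and death to events before the Week 4 primary assessment, for the purpose of primary classification.
- State the precedence: a participant negative at Weeks 2 and 4 with no failure reason by then is a success, whatever happens later. Align footnotes [2] and [3] with it.
- Add to the SAP the Week 4 to 6 failure summary that Protocol 8.1 promises, covering later infections, losses, rescue therapy and deaths by arm.

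The cost is a small wording change in both documents and one added summary, with no new data or participants. The change sets the analysis window only and alters no clinical management.
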